3.2 Secondary Outcome Measures

The secondary outcomes measured will be the total dosage of hypnotic agents administered while in the maintenance phase of anesthesia. These agents include: midazolam, lorazepam, diazepam, fentanyl, sufentanil, ketamine, propofol, morphine, and hydromorphone. Additional secondary outcomes measured will include episodes of hypotension (this will be defined as an episode of mean arterial pressure of <65 mmHg), total dosage of vasopressors (such as phenylephrine, ephedrine, vasopressin, or norepinephrine), and the occurrence of EEG isoelectricity, or burst suppression. SedLine images will be recorded for both groups in order to compare rates and duration of burst suppression events. Of note, if the patient has a functioning arterial line in place, we will use measurements from this in preference to a non-invasive blood pressure cuff).

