12.0 Statistical Considerations

Primary outcome: total average percent of volatile anesthetic (sevoflurane) utilized while subjects are under anesthesia.

Secondary outcomes: total dosage of hypnotic and opioid agents administered while in the maintenance phase of anesthesia. These agents include midazolam, lorazepam, diazepam, fentanyl, sufentanil, ketamine, propofol, morphine, and hydromorphone during the maintenance phase of anesthesia. Additional secondary outcomes measured will include episodes of hypotension, episodes of burst suppression, and total dosage of vasopressors and hypnotic agents.

Statistical analysis will be performed using a standard statistical program (SAS or Stata). All data will be summarized (either means and standard deviations or medians and quartiles for continuous variables; frequencies and percentages for categorical variables) by treatment group. Demographic data will be compared between the two groups using t-test or Wilcoxon rank sum test as appropriate for continuous variables, and chi-square tests or Fisher's exact test for categorical variables as appropriate. The primary outcome, total average percent of volatile anesthetic (sevoflurane) utilized along with secondary outcomes of total dosage of hypnotic agents administered, will be compared between the two groups using t-test or Wilcoxon rank sum test as appropriate. To account for the possible effects of covariates age, sex, and BMI and anesthesiologist, a mixed model with a random effect for anesthesiologists will be employed. Here we could treat surgery type and duration as fixed effects if needed. The secondary outcome of episodes of hypotension which will be compared using chi-square tests or Fisher's exact test for the occurrence of hypotension. Distributions of the continuous variables will be examined, and a transformation of the data (e.g. natural logarithm) or nonparametric tests will be used as necessary. A 5% significance level will be used for all comparisons.

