From a similar study using an outcome (minimum alveolar concentration or MAC) comparable to ours we were able to estimate a coefficient of variation for total average percent of volatile anesthetic to be 0.15.⁴ Working with a feasible sample size of 44 per group and using a power of 90%, 5% significance level, and employing a two-sided test, the study will be able to detect a reduction of 10% in for total average percent of volatile anesthetic between the two groups. Assuming a dropout rate of up to 20%, we will enroll up to 55 patients per group for this study. Here we used a “Tests for the Ratio of Two Means” using sample size software PASS 2019.

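### An unadjusted 5% level covers every secondary comparison, with no hierarchy or exploratory label, so a false positive secondary is several times more probable than the nominal level, though not likely in the benefit direction

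*Combined protocol and SAP*

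**What the plan says.** Section 12.0 names one primary outcome, the mean sevoflurane percentage during maintenance, and ends its analysis paragraph with "A 5% significance level will be used for all comparisons". Neither Section 3.0 nor Section 12.0 gives a testing order or a multiplicity adjustment, or says that secondary outcomes are exploratory. The same sentence also covers the baseline demographic tests.

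The list of secondary outcomes is not fixed:

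- Section 3.2 names the drugs whose dose is recorded: "These agents include: midazolam, lorazepam, diazepam, fentanyl, sufentanil, ketamine, propofol, morphine, and hydromorphone". It adds hypotension, vasopressor dose (four drugs given as examples) and the occurrence of isoelectricity or burst suppression. It also says that SedLine images will be used to "compare rates and duration of burst suppression events".
- Section 12.0 calls the drug outcome hypnotic and opioid dose, lists hypotension, burst suppression and vasopressor dose, and mentions hypnotic dose a second time. It leaves out isoelectricity and the duration of burst suppression.

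Neither section says whether doses are pooled or compared drug by drug. Section 12.0 assigns a between-group test to only two secondaries, hypnotic dose and the occurrence of hypotension.

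**The concern.** The plan is not merely silent on multiplicity. It states a rule, and that rule treats a secondary result at p = 0.04 exactly as it treats the primary. The primary is a drug-dose measure. Hypotension, vasopressor use and burst suppression are the results that a clinician would cite as a gain for the patient. Under the current wording any one of them may be reported as significant without qualification, whatever the primary shows.

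Because the number of secondary tests is not settled, the number of chances to reach p < 0.05 can be settled after the data are seen.

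**Working it through.** **Step 1. The plan's own figure.** Section 12.0 gives these inputs:

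- the variability, as a "coefficient of variation for total average percent of volatile anesthetic to be 0.15"
- group size: 44 evaluable patients in each arm
- target power: 90%
- test: two-sided, at the 5% level
- effect: a 10% reduction, that is, a ratio of means of 0.90

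On the log scale, the SD is √ln(1 + 0.15²) = 0.149 and the difference is |ln 0.90| = 0.105. With the noncentral t distribution, power is 89.9% at 43 per group and 90.6% at 44, so 44 is reproduced. Allowing for 20% dropout, 44 / 0.80 = 55 per group, as stated. The calculation rests on one outcome tested once at 5%, so the secondary tests do not change the primary's error or its sample size.

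**Step 2. How many secondary tests.** The plan gives no number. Three readings of Sections 3.2 and 12.0 are possible:

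- Pooled, 4 tests: hypnotic/opioid dose, hypotension, vasopressor dose, burst suppression.
- Middle, 7 tests: hypnotic dose, opioid dose, hypotension, vasopressor dose, and burst suppression occurrence, rate and duration.
- Everything separate, 9 + 1 + 4 + 3 = 17 tests: nine hypnotic or opioid agents, hypotension, four vasopressors, three EEG measures.

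Baseline comparisons are not counted.

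**Step 3. Chance of at least one false positive.** Assume no effect on any secondary, and two-sided tests (the plan states this only for the primary's sample size). For m independent tests the chance is 1 − 0.95^m in either direction. In the benefit direction each test contributes 2.5%, so the chance is 1 − 0.975^m. For correlated outcomes, equicorrelated normal test statistics with correlation 0.5 were simulated (200,000 runs). The value 0.5 is an assumption.

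| Tests | Either direction, independent | Either direction, corr. 0.5 | Benefit, independent | Benefit, corr. 0.5 |
|---|---|---|---|---|
| 4 | 18.5% | 15.5% | 9.6% | about 8% |
| 7 | 30.2% | 23% | 16.2% | about 12% |
| 17 | 58.2% | 38.6% | 35.0% | 19.3% |

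**Step 4. Size relative to the nominal level.**

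- Either direction, against 5%: 18.5 / 5 = 3.7 times with four independent tests, and 15.5 / 5 = 3.1 times at correlation 0.5.
- Benefit direction, against 2.5%: 9.6 / 2.5 = 3.8 times with four independent tests, and 35.0 / 2.5 = 14 times with 17.
- To pass 50% with independent tests takes 14 tests in either direction, and 28 in the benefit direction.

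**Step 5. Why 17 is a ceiling.** A drug that is seldom used gives a test whose true size is well below 5%. With 44 per arm and an assumed 5% of patients receiving a drug in each arm, Fisher's exact test of use versus no use has a true size of about 0.5%. At an assumed 10% use it is about 1.9%.

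**The case against.** The strongest reply is that the confirmatory claim is already single. Section 2.0 has one primary objective and no secondary objectives, Section 3.1 has one primary outcome, and the sample size is built on that outcome alone. On this view only the labelling of supportive results is missing. This largely stands: the primary is untouched, and the issue is confined to how secondary results are read. It does not remove the point, because the written rule gives those results the primary's 5% level with no label.

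The second reply is that the larger counts are not the plan's. Section 12.0 read plainly gives four outcomes. The vasopressors in Section 3.2 are examples, and Section 5.0 discourages IV anesthetics, including midazolam, during maintenance. Hypotension and vasopressor dose are also plausibly correlated. This stands as well: 58% is an upper limit, not an expected value. Even so, four tests at correlation 0.5 give 15.5%.

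Three stronger readings are tempting, and the documents do not support them:

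- A reader might infer that a false positive benefit is likely. The figures in either direction include apparent harm. In the benefit direction none of the readings reaches 50%.
- A reader might infer that the trial's main conclusion is at risk. It is not, because there is one primary outcome.
- A reader might infer that the sponsor means to claim benefit on a secondary if the primary fails. Nothing in the text says so; the wording merely does not prevent it.

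**Conclusion.** The point holds as a matter of interpreting secondary results, and the change is worth making because it is cheap. If SedLine affects none of the secondaries, the plan accepts about a 19% chance of at least one false positive on the most favorable count (four outcomes), 30% for seven tests and at most about 58% for 17, or 15.5% to 38.6% at correlation 0.5. For an apparent benefit the range is about 10% to 35%, or 8% to 19% at correlation 0.5.

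These figures rest on reconstructed counts, two-sided tests, and one fixed test per outcome. If some secondaries have a real effect, m falls to the number that do not, and the chance falls with it. In the other direction, Section 12.0 leaves open the choice between t-test and Wilcoxon, transformations and some model terms. The figures do not count that flexibility.

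**What to change.** Replace the sentence in Section 12.0 with:

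> The two-sided 5% level applies to the primary outcome. Secondary outcomes and all other comparisons are reported as estimates with 95% confidence intervals and are exploratory.

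That is enough if the sponsor plans no claims on secondaries. If it does, the plan should name in advance one defined measure each for pooled hypnotic/opioid dose (including how doses of different drugs are combined), hypotension, vasopressor dose and burst suppression. These four would be tested with Holm's procedure at 5%, only if the primary is significant. The condition on the primary matters: a separate Holm family at 5% beside a primary at 5% would allow 1 − 0.95² = 9.75% overall if independent. In either case Sections 3.2 and 12.0 should carry the same list of secondary outcomes.

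The cost is an edit to the SAP text and, for the Holm option, four definitions. The sample size stays at 44 evaluable and 55 enrolled per group. The downside is that an isolated secondary with p just below 0.05 can no longer be claimed. Under Holm with four outcomes the smallest p-value must reach 0.05 / 4 = 0.0125.

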13.0 Statistical Data Management

Primary data will be collected via review of electronic medical records, anesthesia records, and screenshot images of the SedLine EEG monitor and will be stored electronically in REDCap. The storage location will be backed up automatically. Quality assurance steps will include, built-in range checks and testing of the database by the study team prior to moving to production mode. The following quality control methods will be used: 1) single data entry with random checks of accuracy; and 2) extraction and cleaning of data that will be used for analysis every 6 months.

14.0 Privacy/Confidentiality Issues

Any private data or potentially identifiable patient data will be stored in the REDcap system.

15.0 Follow-up and Record Retention

The study will start upon approval of the IRB and following selection/training of the anesthesiology study team and the study will stop following completion of data collection from the 110th subject. We anticipate that this should not take longer than 24 months.

